4.3 Testing

Operators are trained in applying the Dräger test according to the instructions for use prior to collecting samples for this study. Training is acknowledged in writing. Patients who consent to participate in this study do not only provide a specimen for their planned PCR testing, but also for testing with the investigational product, the Dräger Antigen Test SARS-CoV-2.

Specimen collection

Trained clinic staff collect specimens for the Dräger test and for RT-PCR. For each sample, they follow instructions for use provided for this study or the site's standard operating procedure (SOP) for the Dräger test and RT-PCR, respectively. Samples are collected and treated as instructed, i.e. the Dräger test is run immediately and read after 15-20 min, while the sample for PCR is stored according to SOP until further processing.

Reading the Dräger Antigen Test SARS-CoV-2 results

The analytical detection limit of the Dräger Antigen Test SARS-CoV-2 is at 250 pg/test, i.e. with ≥ 250 pg of SARS-CoV-2 nucleoprotein present, a test line is visible. The following provides guidance on how to score the Dräger test results. For additional detail refer to the Instructions for Use and the Investigator's Brochure.

Test strips are evaluated 15-20 min after starting the test. The viewing window of the test cassette holds the test strip (Fig. 1, below). One end of the strip is the designated control line area, while the other is the designated test line area. Both areas are indicated with C and T, respectively.

Figure 1. Viewing window with test strip and C and T line area labels; C = control line area, T = test line area.

Positive test result

If red control and test lines are present, the test result is positive. The intensity of the test lines can vary, meaning that very weak, partially colored or broken test lines are also scored as positive.

Negative test result

Test results are read 15 min after starting the test at the earliest and 20 min after starting the test at the latest. If – within this defined window of time – a control line is present while no test line is visible, the test result is negative.

Invalid

If neither a control nor a test line is present within 20 min of starting the test, the result is invalid.

PCR

Samples for PCR are processed in the diagnostics laboratory on site following routine procedures as described in Corman et al. (2020), Lindner et al. (in press), and Matheussen et al. (2020). In brief, the Roche Cobas SARS-CoV-2 assay (Pleasanton, CA United States) is performed.

RT-PCR specific for SARS-CoV-2 and the Cobas PCR assay specifically are considered a suitable reference method because of their e.g. high sensitivity, high specificity, low false-positive rate (Matheeussen et al. 2020, cobas SARS-CoV-2 IFU). As a quantitative assay it delivers information on the viral load for each sample, which allows test performance evaluation in relation to viral load in this study.

4.4 Collection of results

The study staff records patient and testing information (mostly by checking boxes) in the respective CRF:

- Age
- Gender
- Any COVID-19 symptoms? If yes, which and since when?

After Dräger Test specimen collection, the participants indicate the pain level of sample collection (none, light, strong, or unbearable), which is recorded in the CRF. Dräger Test results (positive, negative, or invalid) are entered on the corresponding CRF directly after testing. They are not shared with the participants and do not inform any steps regarding patient/participant management. If feasible, the information is also collected electronically.

PCR samples are processed within 72 h of sampling. PCR results are processed according to the Corona Test Center's regular procedures. They include the information of patients and authorities where applicable. If feasible, the information is also collected electronically.

4.5 Reporting

The PI is responsible for making the following reports available to the Sponsor.

Table 1. Overview

Report	Content
Daily Update	
• No. of participants enrolled• Dräger test results per participant• Information regarding pain and nosebleed• PCR result per participant; as many results as are available at the time of reporting ¹
Weekly Summary	
• Summary of daily data• Symptoms; days since testing (counts for 0-7 days and overall)• Ct value (or viral concentration)• Consent status per patient• AE summary
Half-way Report	
• Due after 425 test result pairs were collected• Content as in Weekly Summary
Final Report	Compilation and review of all

1 – PCR results are provided with a lag time of 1-3 days compared to Dräger test results.

5. DEVIATIONS, ADVERSE EVENTS, AND SAFETY

5.1 Deviations

Deviations are defined as divergences from the Clinical Performance Study Protocol and must be reported and explained. The CRF is the preferred place to indicate a one-time deviation from the standard procedure. Should general (systemic and/or repeating) issues occur and have been identified as such, the PI is to inform the Sponsor's representative immediately. For an overview on documentation and notification requirements see below (p. 13).

5.2 Adverse events

The term adverse event (AE) describes events related to study activities for the performance evaluation of medical devices. It refers to undesirable, negative events such as injuries or diseases observed over the course of the study. General categories are presented and defined in Tab. 2 and Tab. 3, respectively, below.

Table 2. General categories of adverse events as defined by ISO 20916

Adverse events	Non-device-related ¹ - Sampling procedure causes direct harm to participant -	Device-related - Device causes direct harm to user or another person -
Non-serious	Adverse event	Adverse device effect
Serious	Serious adverse event	Serious Adverse device effect Anticipated Unanticipated

1 Note: The Dräger Test kit includes the sampling device, i.e. the sample collector. That means that the sampling – unlike other IVD devices that may require a swab or blood draw – is part of the device-related procedure.

Table 3. Definition of adverse events categories. Definitions apply to studies subject to approval as well as studies with exemption from approval.

AE Category	Definition
Adverse Event, AE	Any untoward medical occurrence, unintended disease or injury in participants, operators or other persons
Adverse Device Effect, ADE	Adverse event related to the use of the Dräger test kit resulting from 
- insufficient or inadequate
o instructions for use,o operation, or- malfunction
Serious Adverse Event, SAE	adverse event (study-related, but not necessarily device -related) that led to any of the following 
- death,- serious deterioration of health of the participant, operator or other persons including but not limited to life-threatening illness or injury,- fetal distress, fetal death or congenital abnormality or birth defect.
Serious Adverse Device Effect, SADE	Adverse device effect that has resulted in any of the consequences characteristic of a serious adverse event (see above)
Anticipated Serious Adverse Device Effect, ASADE	Effect which by its nature, incidence, severity or outcome has been identified in the risk analysis report ¹
Unanticipated Serious Adverse Device Effect, USADE	Serious adverse device effect which is by its nature, incidence, severity or outcome has not been identified in the current version of the risk analysis report

1 See Tab. 4 and Risk Analysis Report for details specific for this study.

Overall, anticipated adverse events have been mitigated based on the current risk assessment (see Tab. 4 below).

Moreover, in an in-house study at Dräger with 46 individuals who were asked to score the experience of specimen collection with the Dräger sample collector as pleasant, neutral, non-pleasant, painful or severely injuring, most participants described it as neutral (Reference 11.5, Report on Usability of Sampling Unit). Two participants scored the sampling as non-pleasant, while nobody reported it as painful or experienced severe injuries. In 1 out of 46 individuals traces of blood were discovered on the sample collector; yet, this individual did not suffer from persistent bleeding after the sampling procedure.

Despite the fact that the nasal sample collection is less common than e.g. nasopharyngeal sampling, the sample collector itself has been used successfully for > 5 years in commercial test kits for saliva collection at the buccal mucosa for abusive drugs testing (Dräger DrugCheck 3000). More than 600000 tests have been sold so far and no complaint has been received with respect to safety issues in this time period. Biocompatibility, cytotoxicity, irritation and bioburden testing attested the sample collector to be safe to use (Reference 11.6, Biocompatibility Synopsis).

Table 4. Anticipated adverse device effects and their respective mitigation for the Dräger test kit

Possible adverse event	Fre-quency	Severity	Risk	Mitigation	Residual risk
Contaminated sample collector	Rare	Catastrophic (depending on the pathogen)	Infection and disease	Special care is taken during production; IFU instructs on hygienic use	None
Investigator/Operator contact with specimen (nasal secretions) of the patient during sampling/Investigator contact with specimen-buffer mix	Rare	Catastrophic (depending on the pathogen)	Infection and disease	Operator wears PPE. Buffer is not harmful. Usual cleaning and disinfection procedures are sufficient. If preferred, a zip loc bag is provided for use during this step.	None
Nosebleed < 15 min	Rare	Non-serious	Injury, pain	Observe the patient closely; if bleeding stops, continue the investigation. If it does not stop after 15 min, participant is transferred to emergency department for appropriate treatment and removed from the study. See also lasting nosebleed below.	None except potential time (< day) in the ER
Lasting (> 15 min) nosebleed requiring intervention	Rare	Non-serious for most patients, serious for patients with bleeding disorder	Blood loss	Exclude patients with bleeding disorder; study staff awareness; Stop of participation in the study for appropriate treatment	None except potential time (< day) in the ER

Pharyngeal swabs are the sampling method for the comparator. As these specimens are not collected exclusively for this study, rather this study uses the results of the current default COVID-19 screening at the site, the procedure is not included in this study's risk assessment.

5.3 Criteria for interruption or early termination of the study:

For the individual participant

If nosebleed occurs in a participant, specimen collection is interrupted until the nosebleed stops. If it stops in less than 15 min, the investigation can continue with the second nostril. An Adverse Device Effect (ADE) is reported in the CRF.

If the nosebleed does continue after 15 min of basic measures, the study investigation is stopped for this participant, and the participant is transferred to the emergency department to respond appropriately to stop the nosebleed. An Anticipated Serious Adverse Device Effect (ASADE) is reported in the CRF and the Sponsor is informed immediately.

If the patient experiences severe pain, discomfort or wants to stop the procedure, the investigation is stopped for this patient and an AE or ADE is reported depending on the evaluation of the study physician.

Participants have the right to withdraw from the study at any time for any reason without penalty or prejudice. The investigator also has the right to withdraw patients from the study if he/she feels it is in the best interest of the patient or if the patient is uncooperative.

For the study in general

- (1) The study stops immediately, if and when approval of the study/exemption of approval by the Authorities or the Ethics Committee is withdrawn or retracted.
- (2) The study is stopped early, if > 10% of participants experience lasting nosebleed (longer than 15 minutes) or unbearable pain. This assessment starts with the first 50 participants enrolled. See also 7. Monitoring below.
- (3) The Sponsor reserves the right to discontinue the study at any time in its entirety e.g. if, in the sponsor's opinion, there is a significant safety concern, relevant technical problems with the device or an insufficient recruitment despite intensified efforts to screen potential participants. See also 7.4 Monitoring below.

5.4 Documentation requirements

All unexpected observations and/or adverse events must be reported and documented on the CRF by Operator and Principal Investigator (PI) (Tab. 5).

The PI has the responsibility to document and explain any deviations or adverse events, actions taken, and notify the sponsor represented by a designated Project Lead (refer to 9.1 Site and Sponsor Representatives for details).

5.5 Notification requirements

The table below describes the PI's responsibilities regarding Sponsor notifications.

Table 5. Event documentation and sponsor notification

Event	Document on CRF	Notify via E-mail	Notification Timing
Deviation	yes	Sponsor's Representative	Within two weeks
AE, ADE	yes	Sponsor's Representative	Within two weeks
SAE, SADE	yes	Sponsor's Representative	Immediately; at the latest within 24 h
ASADE, USADE	yes	Sponsor's Representative	Immediately; at the latest within 24 h

The Sponsor informs the Competent Authority in case of SAEs via e-mail to [contact].

6. STATISTICAL AND ANALYTICAL CONSIDERATIONS

All cases are included in the overall analysis and evaluation of the study and in the resulting report.

In general, numbers of participants (eligible, enrolled, included in analysis), Dräger test and PCR results, invalid tests, dropouts at every level, deviations, AEs etc. are recorded, monitored throughout the study, and reported in the final study report. Performance data is presented in the context of these counts. Only cases for which both a valid Dräger test and a valid PCR result are available are included in the determination of performance parameters such as sensitivity and specificity (see below). In addition, the following information is required for a case to be included, i.e. a case is excluded should the following information not be documented:

- Participant ID
- Participant provided written informed consent.
- Information regarding any pain sensation
- Information regarding nosebleed
- Information regarding adverse event (on the level of yes or no)

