2. STUDY DESIGN

The study is designed as a prospective, monocentric, clinical performance evaluation study. It is designed to demonstrate suitability of the Dräger Antigen Test for SARS-CoV-2 nucleoprotein detection in clinical nasal specimens. Real-time reverse transcriptase polymerase chain reaction (RT-PCR, here also short PCR) on specimens collected by pharyngeal swabs serves as a reference method for all participants of this study. In fact, participants are recruited from people presenting themselves for SARS-CoV-2 testing (pharyngeal swab and PCR) at designated testing locations of the study site. Each participant must meet all inclusion criteria of the respective group (i.e. symptomatic or asymptomatic). For details on the reference method and scoring (cut-off) refer to 4.3 and 6.2 below.

The goal of the study is to compare Dräger test results to the corresponding PCR data for overall sensitivity and specificity. Assuming a 20% PCR positive rate at the study site (prevalence), a 90% Dräger test sensitivity as the expected sensitivity, allowing room for

dropouts, and ensuring inclusion of at least 100 asymptomatic cases approx. 850 participants have to be enrolled (for details see case number estimation in 6).

Dräger provides approximately 900 Dräger test kits for this study to allow for practice runs and error. Should more testing become necessary after review of the half-way point or the endpoint, plans are made accordingly. When 425 data pairs of Dräger test and PCR results are available, the study reaches its half-way point. All data relevant for overall sensitivity and specificity are analyzed, and a brief overview of results serves as a preliminary summary at this point of time. Data relevant for secondary objectives are analyzed at the end of the study.

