4.2 Inclusion and Exclusion Criteria

If inclusion criteria are not met, the participant is excluded from the study.

Inclusion criteria of individuals

- Participants must require SARS-CoV-2 testing for the following reasons:
 - COVID-19 symptoms (Fever, cough and/or sore throat, fatigue/ general feeling of weakness, loss of sense of smell and/or taste, shortness of breath, muscle stiffness/ body aches, head cold/ running nose, etc.) on the day of testing, or
 - Known or suspected exposure to SARS-CoV-2 (contact persons etc.), or
 - Member of a group of high risk of exposure such as healthcare workers etc., or
 - Require screening for any other reason, e.g. doctor's orders, hygiene directive etc.
- Participant must be of legal age and must be able to understand the procedure and letter of consent.
- Patient provides written consent prior to enrollment.

Exclusion criteria of individuals

- Persons younger than 18 years old are excluded from the study.
- Pregnant or breastfeeding women are excluded from the study.
- Persons unable to provide written informed consent are excluded.
- Persons with bleeding disorder are excluded from the study as a precaution.
- Persons in institutions where they are (involuntarily) held due to an official order or a court order are excluded from the study.
- Hospitalized patients/inpatients are excluded.
- Application of nasal spray within 15 min prior to testing.
- Participants with symptoms on the day of testing are excluded, if any of their symptoms started more than 7 days prior to testing.
- Asymptomatic participants are excluded, if they experienced any symptoms in the 14 days prior to testing.

Inclusion of Dräger test samples/data

All data is presented and assessed in the study report. Only results with both valid Dräger test and valid PCR results are included in the data set for clinical performance assessment. A Dräger Antigen Test SARS-CoV-2 result is valid when:

- Pouch intact upon visual inspection,
- Desiccant bag present,
- Kit not expired,
- All components (sample collector, test cassette) present,
- Kit appears undamaged and ampoule is intact (no leaking apparent),
- Indicator ring is colored prior to testing,
- Results were read according to this study protocol.

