6.1 Case number estimation

For the case number estimation for the primary endpoint the following assumptions are made:

Sensitivity:

Lindner et al. (in press) collected samples from the anterior nose and observed 27 of 29 SARS-CoV-2 PCR-positive samples ($> 10^6$ copies/mL) to also be rapid antigen test-positive (93.1% agreement). The case number estimation for the Dräger Antigen Test SARS-CoV-2 is based on a more conservative expectation of 90% sensitivity. This assumption is based on preliminary performance data of the test under evaluation and the threshold for PCR set to 10^6 copies/mL (refer to 6.2 for details).

The half width of the confidence interval (W) is pre-determined at 5%, as $90\% \pm 5\%$ provides sufficient test reliability for a daily application in the clinical setting. A test sensitivity of 85% would still meet the PEI criterion for antigen tests (sensitivity $> 80\%$; PEI, 2021).

Specificity:

Lindner et al. (in press) observed a rapid antigen test specificity of 99.6% (95% CL, CI 97.8-100.0%) in anterior nasal swabs. As a result, the investigational product is expected to be 99% specific. For diagnostic applications, a device should deliver a specificity of 99% with a precision of $\pm 1\%$ in order to be of service, e.g. in the screening of symptomatic patient at times of high incidence. It also needs to be taken into account that the intended use of the investigational product is for screening; ultimate confirmation of the preliminary result remains for more sensitive PCR testing.

Separate calculations for case numbers for sensitivity and specificity of the test are performed following the approach by Hajian-Tilaki (2014). The following formulae are used:

$$N(SN) = z^2 \times \frac{(SN(1 - SN))}{W^2 \times P}$$
$$N(SP) = z^2 \times \frac{(SP(1 - SP))}{W^2 \times (1 - P)}$$

with

- N = Case Number
- SN = Sensitivity
- SP = Specificity
- z = z-value corresponding to a confidence level of 95%
- P = Prevalence of disease in the test population. Prevalence is assumed to be at least 20% based on current data from the prospective study sites indicating an actual prevalence among all participants tested for SARS-CoV-2 of 25%.
- W = maximum marginal error (half width of 95% confidence interval) for sensitivity and specificity, respectively

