6.3 Assessment of primary objective

Dräger test and PCR results for all participants are recorded. All valid data pairs (valid Dräger test result, valid PCR result, complete records as defined on pp. 13) from the symptomatic group feed into sensitivity and specificity evaluation of the Dräger test. A contingency table is used to present sensitivity, specificity, and associated confidence intervals (CI at a confidence level of 95%).

Table 7. Assessment of results.

Dräger Antigen Test SARS-CoV-2 result	Reference method RT-PCR result	
	Positive	Negative
Positive	True positive (TP)	False positive (FP)
Negative	False negative (FN)	True negative (TN)

Key parameters to be determined:

$$\text{Sensitivity} = \frac{\text{TP}}{\text{TP} + \text{FN}} \times 100$$

$$\text{Specificity} = \frac{\text{TN}}{\text{FP} + \text{TN}} \times 100$$

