6.4 Assessment of secondary objectives

Secondary endpoints are of explorative nature and descriptive statistics are used for evaluation (mean, median, minimum, maximum, frequencies, standard deviation, 95% CL confidence limits).

All valid data pairs (valid Dräger test result, valid PCR result, complete records) feed into sensitivity and specificity evaluation of the Dräger test. Sensitivity and specificity including lower and upper confidence limits for the test under evaluation are calculated for different cut-offs of the ct value of the PCR test in addition to the predefined ct value for the primary endpoint (currently defined by a viral concentration of 10^6 RNA copies/mL and to be calibrated to ct). Prerequisite for inclusion in this explorative evaluation is that the case record is not only complete as defined above, but also provides the information required to allow sorting into groups according to e.g. ct values.

Sensitivity and specificity including lower and upper confidence limits for the test under evaluation are calculated for participants grouped by

- ct value (as described above),
- time since symptoms onset (using the general cut-off ct value of the PCR test used for the primary endpoint evaluation; on symptomatic group only),
- symptom status (symptomatic vs asymptomatic).

In addition to sensitivity and specificity centric explorative evaluation, the frequency of lasting nosebleeds or unbearable pain in participants is tracked. The primary information is captured in the CRF. Once the 50 participants have been enrolled the fraction of participants reporting such experiences is determined daily.

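### Valid test pairs are dropped from sensitivity and specificity when pain, nosebleed or adverse-event fields are blank, although these fields play no part in classifying a case

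*Combined protocol and SAP*

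**What the plan says.** Section 6 sets the base rule: "Only cases for which both a valid Dräger test and a valid PCR result are available are included in the determination of performance parameters". It then adds a second condition, that "a case is excluded should the following information not be documented". Five items follow: participant ID, written informed consent, "Information regarding any pain sensation", nosebleed, and adverse event as yes or no.

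The condition reaches every accuracy estimate:

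- **Section 6.3 (primary objective)** admits symptomatic pairs with "complete records as defined on pp. 13".
- **Section 6.4 (secondary objectives)** requires that "the case record is not only complete as defined above, but also provides the information required to allow sorting into groups".

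Section 4.2 describes the same data set without the condition: "Only results with both valid Dräger test and valid PCR results are included in the data set for clinical performance assessment". It is less complete than section 6 but does not contradict it.

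Section 6.2 and Table 7 in section 6.3 define true and false positives and negatives by setting the Dräger result against the PCR result at the 10^6 copies/mL threshold. No other field enters.

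**The concern.** Participant ID and consent are proper conditions for using a record. Pain, nosebleed and adverse-event status are not needed to place a case in Table 7, and they are not among the Dräger validity criteria in section 4.2. They serve the tolerability objective (sections 3.2 and 6.4) and the study stopping rule (sections 5.3 and 7.4). The plan gives no reason for tying accuracy to them.

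Two things are at stake. The first is precision: the sample size for sensitivity has almost no slack at the planned 20% prevalence, so any further loss of reference-positive pairs widens the interval. The second is selection: if blank fields were related to the test results, the estimates would shift, and no supplementary analysis adds the dropped pairs back.

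**Working it through.** **Inputs.** From section 6.1: sensitivity 90% with half width 5 points, specificity 99% with half width 1 point, 95% confidence (z = 1.96), prevalence at least 20% with 25% currently observed, 5% dropout, and totals of 691, 726, 105 and 831. From section 2: about 850 enrolled. The blank rate is not given, so 1%, 2% and 5% are assumptions.

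**The plan's own figures.**

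- Sensitivity: N = 1.96² × 0.90 × 0.10 / (0.05² × 0.20) = 691.5, stated as 691. With dropout, 691 × 1.05 = 725.6, stated as 726.
- Specificity: N = 1.96² × 0.99 × 0.01 / (0.01² × 0.80) = 475.4. With dropout this is 499 to 501, depending on the inflation method, stated as 500.

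All three reproduce. Reference-positives needed for 5 points at 90%: 1.96² × 0.09 / 0.05² = 138.3.

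**Pairs lost.** Of 691 pairs, blank rates of 1%, 2% and 5% remove 6.9, 13.8 and 34.6. Of 138 reference-positives they remove 1.4, 2.8 and 6.9.

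**Sensitivity half width** = 1.96 × √(0.09 / n), in percentage points:

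| Scenario | Reference-positives, no loss | No loss | 1% | 2% | 5% | Target passed above |
|---|---|---|---|---|---|---|
| (a) 691 pairs, 20% | 138 | 5.01 | 5.03 | 5.06 | 5.14 | already at target |
| (b) 850 enrolled, 20% | 141.6 | 4.94 | 4.97 | 4.99 | 5.07 | 2.3% |
| (c) 691 pairs, 25% | 172.8 | 4.47 | 4.50 | 4.52 | 4.59 | 19.9% |

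- (a) The 5.01 with no loss comes from rounding 691.5 down to 691.
- (b) This assumes that the 19 participants above 831 are symptomatic: (850 − 105) × 0.95 × 0.20 = 141.55. Break-even: 1 − 138.3/141.55 = 2.3%.
- (c) 691 × 0.25 = 172.75. Break-even: 1 − 138.3/172.75 = 19.9%. The documents do not say what share of the 25% lies at or above 10^6 copies/mL, so this row may be optimistic.

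**If blanks fall inside the 5% dropout allowance:** 726 × 0.95 × 0.20 = 137.9 reference-positives and a half width of 5.01. The planned precision does not change.

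**Specificity half width** = 1.96 × √(0.0099 / n): 0.83 points at n = 553 (80% of 691) and 0.85 at n = 525.4 (5% loss), against a target of 1.

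**Selection, as a constructed extreme.** With 138 reference-positives and 14 false negatives, sensitivity is 124/138 = 89.9%. Losing three pairs that are all false negatives gives 124/135 = 91.9%. Losing three that are all true positives gives 121/135 = 89.6%. This shows the sensitivity of the estimate to selective loss, not an expected result.

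**The case against.** The strongest reply is that this is a pre-specified, visible complete-record rule with a negligible expected effect.

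- **Blanks should be rare.** CRF entries are mostly tick boxes (section 4.4), operator and investigator confirm completeness and may correct entries (section 7.2), and pain and nosebleed are reported to the sponsor daily (section 4.5).
- **Exclusions are counted.** Section 6 requires dropouts at every level to be reported alongside performance.
- **The loss may be counted twice.** Scenario (a) takes blanks off after the dropout allowance, which could be read to cover incomplete records.
- **A shortfall could be made up.** Section 2 allows for more testing, and the synopsis lets screening be extended.
- **The consequence is minor.** A 5% blank rate moves the lower limit at 90% sensitivity from about 85.0% to about 84.9%, against the criterion of more than 80% cited in section 6.1.
- **Selection is implausible.** Pain is recorded just after sampling, and PCR results follow 1 to 3 days later, so a case's classification is normally unknown when the fields are filled in.

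Most of this stands, and it keeps the concern small. It does not supply a reason for the rule. Counting exclusions does not restore the estimate, and the documents do not say that the dropout allowance covers incomplete records. The timing argument is good but not complete: the Dräger result is on the same CRF, and section 7.2 sets no deadline for corrections, so blanks could be chased after results are known.

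It can also be argued that nosebleed or pain shows whether sampling ran normally, since section 5.3 provides for interrupting or stopping collection. But the rule removes cases where these fields are undocumented. A case with a documented nosebleed or severe pain and a valid pair stays in. The rule is therefore no check on sampling quality.

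**Conclusion.** The concern holds. The plan makes inclusion in the primary and secondary accuracy estimates depend on three fields that have no role in those estimates. The likely effect is small: at most about 0.13 points on the sensitivity half width (5.01 to 5.14) at an assumed 5% blank rate beyond dropout and 20% prevalence, nothing if the dropout allowance absorbs the blanks, and no threat to the specificity target. Bias in either direction is possible in principle, but no mechanism is shown. The case for change rests on avoidable loss of valid primary data at almost no cost, not on demonstrated harm. The size depends on a blank rate that the documents do not give.

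**What to change.** In section 6, remove pain, nosebleed and adverse-event documentation from the conditions for the performance set, and keep participant ID, documented consent, a valid Dräger result and a valid PCR result. Apply the three fields only to the denominators of the tolerability frequencies in section 6.4. That section already uses the same principle when it asks for grouping information only in the analyses that need it. Align sections 4.2, 6.3 and 6.4 to this one definition, and report the number of cases with a blank tolerability field.

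The cost is a short wording amendment, possibly with Ethics Committee review (section 8), and separate denominators for performance and tolerability in place of one common set. No extra participants or data are needed. If the sponsor prefers to keep the rule, the minimum is to report the valid pairs dropped solely for these fields and to give a supplementary estimate that includes them.
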